Patients may be approached for the study in various way including clinic intercepts, study flyers and clinic referrals. The electronic health record will be queried to identify potentially eligible participants using the inclusion/exclusion criteria. Providers (including but not limited to physicians, nurse practitioners, and pharmacists) who care for patients at UF Health will be notified when their patients qualify for the study and will be asked to discuss the study with their patients.

Patients can be recruited by study staff via two methods:

1. Clinic providers or staff ask patients if they are interested in participating and they acknowledge that they are interested.
2. Clinic provider or staff will provide patients an approved flyer and they contact study staff if interested.

If recruitment occurs during a clinic visit, patients meeting eligibility criteria will be approached by a research coordinator about study participation. Patients may also be contacted via phone after their clinic visit if in-person contact is not possible (for example, but not limited to, space limitations due to COVID-19 restrictions).

A research coordinator will review the consent document with the patient prior to enrollment. The consenting process can be in-person or remote via telephone or through electronic means. Prospective research participants will have the opportunity to ask questions before providing consent and will be provided with a signed copy of the consent form.

After providing written informed consent, a DNA sample will be collected from all patients by saliva (via mouthwash swish and expectorate collection) or buccal cell (via buccal brush/swab). If the genotyping fails with initial sample collection, the patients may be mailed a DNA collection kit for saliva or buccal cell sample collection for retesting.

Study design. After eligible participants provide written informed consent and are enrolled, a DNA sample will be obtained for PGx testing and questionnaires (as described below) will be administered at baseline, and then again at 3 months and 6 months after PGx results are entered into the EHR. Information will be abstracted from the EHR including PGx test results, medication changes, and healthcare provider encounters over the 6-month study duration (Table 1). A 1-month window will be permitted for each follow-up study interaction (\pm 15 days of exact due date).

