PGx testing will be completed using the GatorPGx panel, which is already available for clinical use in the CAP/CLIA certified UF Molecular Pathology Laboratory. Once results are entered into the EHR, Clinical Decision Support Best Practice Advisories already built into Epic will alert providers if a PGx interaction

might occur with a medication they prescribe. All clinical medication decisions will be made at the discretion of the healthcare provider.

Feasibility data collection:

The primary feasibility outcome will be change in patient treatment satisfaction between baseline and 6 months after PGx testing. This patient reported outcome will be measured via the Treatment Satisfaction Questionnaire for Medication (TSQM). The TSQM is a validated tool that assesses three medication-related domains (effectiveness, side effects, and convenience) to synthesize a global satisfaction score.^{5,6} Both global satisfaction and scores from individual domains will be analyzed.

Table 1. Proposed outcomes/measures to be tested

Outcome/Measure	Data source/Instrument	Ascertainment method	Baseline	3 mo.	6 mo.
Implementation Outcomes					
Treatment satisfaction	Treatment Satisfaction Questionnaire for Medication (TSQM)	Online or by phone	X	X	X
Medication adherence	Adherence Questionnaire	Online or by phone	X	X	X
Perceived value	Patient reported value	Online or by phone	X	X	X
Time discussing meds w/ healthcare provider	Patient reported estimate	Online or by phone	X	X	X
Effectiveness Outcomes					
Medication changes	EHR data	EHR data pull	X		X
Provider encounters	EHR data	EHR data pull	X		X
Socioeconomic Measures					
SEI	Patient report	Online or by phone	X		
Occupation	Patient report	Online or by phone	X		
Education level	Patient report	Online or by phone	X		
Household Income	Patient report	Online or by phone	X		
Household zip code	Patient report	Online or by phone	X		

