An important secondary outcome assessing efficacy will include the number of medication changes within the 6-month follow-up period. Medication changes will be defined as the addition, removal, or dosage change to any PGx medication or medication within the same drug class. Comparisons of this outcome should estimate differences in trial-and-error drug dosing that is traditionally used in practice. These outcomes are important because if the results suggest that preemptive PGx testing is associated with increased patient treatment satisfaction, a reduction in medication changes, or increased perceived value of PGx testing, these findings would support expanded clinical implementation in medically underserved patients. This might also suggest that PGx could be further used as a tool to minimize disparities in pharmacotherapy. Other secondary outcomes that will be analyzed include: The prescriber acceptance rate of PGx EHR alert recommendations, number of encounters with a healthcare provider over the study period, genotype turnaround time, and estimated time spent discussing medications with a healthcare provider. These outcomes will be used to assess feasibility and will inform design of a large clinical trial to be funded by future grants.

Socioeconomic data collection: We have previously observed significant associations between calculated geographic access scores and rate of PGx drug prescriptions, which considerably strengthened in subanalyses by race. Whether this association is exclusively related to geography and race or whether it is also related to socioeconomic determinants is unknown. Thus, we will test whether socioeconomic status is a social determinant of health related to PGx drug usage. Patients will answer survey questions related to their education, employment, and income (Table 1).

Qualitative data collection: An estimated sample size of 20 patients from the 100 recruited participants will be recruited for this aim. Patient sampling will be aimed at achieving an approximately even distribution of sex (male and female) and race (Latino and black).

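### A before/after fall in PGx-related medication changes cannot by itself be read as less trial-and-error prescribing

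*Combined protocol and SAP*

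**What the plan says.** Section 6, Feasibility data collection, names as an important secondary outcome the "number of medication changes within the 6-month follow-up period" and defines it: "Medication changes will be defined as the addition, removal, or dosage change to any PGx medication or medication within the same drug class". The definition does not record why a change was made. The next sentence gives the intended reading: "Comparisons of this outcome should estimate differences in trial-and-error drug dosing that is traditionally used in practice". The protocol then lists signals that would favour wider use, among them "a reduction in medication changes, or increased perceived value of PGx testing, these findings would support expanded clinical implementation".

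Other parts of section 6 bear on this:

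- **Inclusion Criteria**, item 3, requires a medication change in the past 6 months, tied to a provider encounter. It is not restricted to PGx drugs.
- **Exclusion Criteria** remove anyone with earlier PGx testing in the EHR.
- **Study design** starts the alerts only after testing: "Once results are entered into the EHR, Clinical Decision Support Best Practice Advisories already built into Epic will alert providers" if an interaction "might occur with a medication they prescribe". The data abstracted are "medication changes, and healthcare provider encounters over the 6-month study duration".
- **Table 1** marks EHR pulls for this outcome at baseline and 6 months, with no look-back length for the baseline.
- **Analysis plan** compares the effectiveness outcomes between baseline and 6 months by Student's t-test or Mann-Whitney U test, then by regression, at two-sided 0.05. All 100 patients are tested, and no untested group is described.
- "The prescriber acceptance rate of PGx EHR alert recommendations" is a separate secondary outcome, summarised descriptively and not linked to the count.

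**The concern.** Two features separate the total from what it is said to measure, and they pull in opposite directions.

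First, patients enter because they had a recent medication change. If the baseline count looks back over the same 6 months, patients are selected on something related to their baseline value. No such selection acts on follow-up, so the count can fall with no effect of testing. Without an untested group, that fall cannot be told apart from a benefit. None of the covariates named as examples for the regression addresses it.

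Second, a change prompted by a PGx alert can occur only after results are in the record, and it scores the same as a trial-and-error change. If alerts lead to additional changes in existing therapy, the intervention doing its job adds to the count that is meant to fall.

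Followed as written, the plan could credit testing with a fall that the entry rule produced, or miss a real one. The protocol says these outcomes will inform a larger trial, so a misreading could carry forward.

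**Working it through.** The plan gives no change rate, PGx share, actionable-genotype rate or acceptance rate for this outcome, so there is no stated figure to reproduce. From the documents come n = 100, two-sided 0.05, the 6-month entry window and the 6-month follow-up. Everything else below is assumed.

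**Entry rule, one shared rate.** Let B be the true PGx-related changes per patient per 6 months and p the share of all medication changes that are PGx-related. Assume all changes are Poisson with mean B/p, entry needs at least one, and the baseline look-back equals the entry window. Then:

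- expected baseline = B / (1 − exp(−B/p)), and expected follow-up with no effect = B
- excess = B / (exp(B/p) − 1)
- apparent relative fall = exp(−B/p)

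Example: p = 0.5, B = 0.5 gives 0.5 / (e − 1) = 0.29, a fall of exp(−1) = 37%.

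Each cell shows the excess, the apparent fall, and the proportion of simulated 100-patient trials with a significant fall (paired t-test, no true change, no alert-linked changes; nominal 2.5% in that direction).

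| PGx share p | B = 0.5 | B = 1 | B = 2 |
|---|---|---|---|
| all | 0.77; 61%; 100% | 0.58; 37%; 99% | 0.31; 14%; 37% |
| half | 0.29; 37%; 80% | 0.16; 14%; 20% | 0.04; 2%; 4% |
| quarter | 0.08; 14%; 12% | 0.02; 2%; 4% | 0.00; 0%; 3% |

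**Entry rule, rates that vary between patients.** Patients will not share one rate. Let the rates follow a gamma distribution with shape 1 and population mean L = B/p. The excess becomes p/(1 + L) and the relative fall 1/(1 + L)².

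- Half share, B = 0.5 (L = 1): excess 0.5/2 = 0.25, fall 1/4 = 25%. A significant fall appears in about 51% of trials by paired t-test, about 40% by unpaired t-test and 68% by Mann-Whitney.
- Full share, B = 2 (L = 2): excess 1/3 = 0.33, fall 1/9 = 11%. This excess is slightly above the 0.31 in the table, so the one-rate excesses are not upper limits. Here the paired test gives about 32% and the unpaired about 6–7%. The choice of test matters, and the Analysis plan does not say which form applies.
- Quarter share, B of 1 or 2: about 5% or less by either t-test.

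**Alert-linked changes.** Let A be the additional follow-up changes per patient that alerts cause in existing therapy. The share of a true 20% fall that is hidden is A / (0.20 × B). A middle case takes 30% of patients with an actionable result, 50% acceptance and 50% of accepted alerts on existing therapy: A = 0.30 × 0.50 × 0.50 = 0.075 if every such change is additional and counted once.

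- B = 0.5: 0.075/0.10 = 75% hidden
- B = 1: 0.075/0.20 = 37.5%
- B = 2: 0.075/0.40 = 18.75%

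If only half of these changes are additional, the figures halve. If alerts act only on new orders, A = 0.

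**Both together.** With no true change the net is A − excess. Take B = 1, A = 0.075 and the one-rate model. At half share the net is 0.075 − 0.157 = −0.082; at quarter share it is 0.075 − 0.019 = +0.056. Even the sign depends on a share that the documents do not give.

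**The case against.** Both mechanisms are conditional. An alert tied to a medication being prescribed reads most naturally as acting on a new order. Redirecting that order still counts as one addition, so nothing is added to the total. Patients must be on at least one panel drug, which makes changes to existing therapy possible, but no text says that existing therapy or renewals trigger alerts. The qualifying change at entry need not involve a PGx drug, and the baseline look-back may not overlap the entry window. In several of the cases shown, the entry effect is close to nothing. All of this stands.

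The plan's claim is also modest. It speaks of association, lists the reduction as one of three alternative signals, keeps treatment satisfaction as primary, and reports prescriber acceptance, which tells readers something about alert-driven action. This limits the weight of the point. It does not remove it, because the stated reading of the count has no caveat and the acceptance rate is not connected to the count.

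A reader might infer that the comparison is biased towards a fall, or that alerts will push the count up despite a real benefit. The documents support neither: they give no rates and do not describe what triggers an alert. The 80% figure should likewise not be taken as the trial's false-positive rate. It depends on one shared rate, few changes per patient and a matching look-back.

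**Conclusion.** The point holds in a limited form. A before/after reduction in the total is not by itself evidence of less trial-and-error prescribing, and a rise or no change is not by itself evidence against it. The size and net direction of the distortion are unknown, and either part may be near zero. In the illustrations, the chance of a spurious significant fall runs from about nominal to very high, depending on the change rate, the PGx share, variation between patients and the test used. Those illustrations assume a 6-month baseline look-back that matches the entry window.

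The unstated look-back and the missing rule for a same-class switch (addition and removal are listed separately, so it could count as one event or two) are gaps in specification. Alone they would be missing detail; here they also decide how far the two effects operate. This is one secondary outcome in a 100-patient pilot. It is worth correcting because the protocol uses it to support expansion and to inform a larger trial.

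**What to change.** 1. In section 6, Feasibility data collection, state that a reduction in the total is not by itself evidence of less trial-and-error prescribing, because of the entry rule and alert-linked changes. Do not count it alone as support for expansion. This is the core change.
2. Keep the total as the before/after comparison, with the same stated look-back length and the same rule for counting a same-class switch in both periods.
3. Where the alert records used for the acceptance rate allow it, label each follow-up change as either an alert-linked change to existing therapy or other. Report both descriptively beside the total. Do not test the 'other' count against the unsplit baseline, since the two are not like for like.

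The first two items cost a few sentences. The third needs a simple attribution rule and a link between EHR medication changes and alert records. Neither the abstraction list under Study design nor Table 1 includes alerts, so their availability at the level of single changes must be confirmed. No new data are needed from patients. The split has limits: some alert-linked changes might have happened anyway, and it does not remove any inflation from the entry rule. Only the limit on the conclusion deals with that.

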Analysis plan. For Aim 1, implementation outcomes such as prescriber acceptance, turnaround time, and cost will be assessed using descriptive statistics. Differences in patient reported outcomes such as treatment satisfaction, perceived value, and effectiveness outcomes (Table 1) will be initially compared between baseline and 6 months using Student's t-test or Mann-Whitney U test, depending on the data distribution. In addition to univariate analyses, multiple regression models will also be completed for each outcome, adjusted for potential covariates, such as age, race, sex, clinic site, and Charlson Comorbidity Index. In all analyses, a two-sided $P \leq 0.05$ will be considered statistically significant, and all statistical analyses will be completed in R ver. 3.6.3.

For Aim 2, interview transcripts will be managed using data management software (e.g., Nvivo or Atlas.ti). Data will be thematically analyzed using the widely used constant comparative method.¹³ This systematic approach involves several coding steps including identifying concepts and assigning codes, 2) grouping categories of emergent themes, and 3) axial coding to identify thematic properties. To ensure similarities and differences between patients' experiences can be captured, data analysis will be segmented by group and triangulated with survey data collected from healthcare providers (via separate protocol). Triangulation of data between sources also enhances the validity of the findings.¹⁴ Multiple coders, trained in the CCM approach, will conduct the analysis to ensure rigor. Meetings will be held to compare independent coding, discuss differences in interpretation, collapses analyses, and continuously refine the codebooks. Codebooks will be developed with each stakeholder group dataset. Once codebooks are finalized and analyses complete, each analysis will be validated by an additional coder analyzing a subset of the transcripts from each group.¹² Operational and thematic memos will be maintained across data collection and analysis to ensure researcher reflexivity, thematic saturation, and rich description of themes.

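### Three outcomes joined by 'or' can each support wider implementation, although only satisfaction is primary, no single TSQM score is named and no multiplicity control is stated

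*Combined protocol and SAP*

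**What the plan says.** All of this is in section 6, Research Plan.

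- **One primary outcome.** Feasibility data collection: "The primary feasibility outcome will be change in patient treatment satisfaction between baseline and 6 months after PGx testing". It is measured with the TSQM, which has three domains and a global score.
- **Four scores, none singled out.** The same paragraph adds: "Both global satisfaction and scores from individual domains will be analyzed".
- **Medication changes are secondary.** The text after Table 1: "An important secondary outcome assessing efficacy will include the number of medication changes within the 6-month follow-up period". Perceived value is listed in Table 1 as an implementation outcome, but it is neither the stated primary nor in the text's list of secondary outcomes.
- **Three routes to one conclusion.** The same paragraph says that if testing "is associated with increased patient treatment satisfaction, a reduction in medication changes, or increased perceived value of PGx testing", then "these findings would support expanded clinical implementation in medically underserved patients". It closes by saying that the outcomes serve to assess feasibility and to help design a larger trial.
- **One threshold.** Analysis plan: "In all analyses, a two-sided $P \leq 0.05$ will be considered statistically significant". Outcomes "will be initially compared between baseline and 6 months using Student's t-test or Mann-Whitney U test, depending on the data distribution", and each is also analysed in a covariate-adjusted regression.

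The document states no hierarchy, testing order or multiplicity adjustment.

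**The concern.** Naming a primary outcome is meant to fix in advance which result carries the conclusion. Here two of the three results that may carry it are not the primary. The primary itself can be read from any of four scores. If satisfaction does not change but perceived value rises, or medication changes fall, the plan's own wording still allows a favourable statement about implementation.

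That statement is an intended use of the data, not an isolated remark: the Abstract also expects the results to support wider implementation of testing in underserved patients. What is at stake is the error rate behind such a statement. It is no longer that of one pre-named test, and a reader of the report could not tell from the protocol how many chances there were.

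**Working it through.** The documents give no family-wise error rate, power or sample-size derivation, so there is no stated figure to reproduce.

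**Inputs from the documents**
- Level: 0.05 two-sided for every analysis (Analysis plan), which is 0.05 / 2 = 0.025 per test in the favourable direction.
- Outcomes joined by 'or': 3.
- Scores within satisfaction: 1 global + 3 domains = 4. If every score counts, the number of tests is 4 + 1 + 1 = 6.

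**Assumptions**
- The P ≤ 0.05 threshold is what decides whether a result counts as support.
- Each test holds its nominal level.
- The documents give no correlations between test statistics, so a range is shown.

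**Formulas.** For k independent tests, the chance of at least one favourable significant result under no effect is 1 − 0.975^k; for a significant result in either direction it is 1 − 0.95^k. Under any correlation, neither can exceed k times the single-test rate. Correlated cases use multivariate normal test statistics with cut-off 1.96.

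**Three tests** (satisfaction as one score, medication changes, perceived value)

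| Common correlation | Any favourable | Multiple of 2.5% | Either direction | Multiple of 5% |
|---|---|---|---|---|
| 0 | 1 − 0.975³ = 7.3% | 2.9 | 1 − 0.95³ = 14.3% | 2.9 |
| 0.3 | 6.8% | 2.7 | 13.6% | 2.7 |
| 0.5 | 6.3% | 2.5 | 12.5% | 2.5 |
| 0.7 | 5.5% | 2.2 | 10.9% | 2.2 |

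Ceiling for three tests: 3 × 2.5% = 7.5% favourable and 3 × 5% = 15% in either direction.

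**Six tests** (four TSQM scores, medication changes, perceived value)

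| Correlation among TSQM scores | All other correlations | Any favourable | Multiple of 2.5% | Either direction |
|---|---|---|---|---|
| 0 | 0 | 1 − 0.975⁶ = 14.1% | 5.6 | 1 − 0.95⁶ = 26.5% |
| 0.3 | 0 | 13.3% | 5.3 | 25.5% |
| 0.5 | 0 | 12.3% | 4.9 | 23.8% |
| 0.7 | 0.2 | 10.7% | 4.3 | 21.1% |
| 0.8 | 0.2 | 9.9% | 4.0 | 19.6% |

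**If the tests do not hold their level.** The Analysis plan names Student's t or Mann-Whitney U for before/after data and does not say that the t-test is paired. A two-sample z-type test on pairs with within-patient correlation r has two-sided size 2 × [1 − Φ(1.96 / √(1 − r))]. At an assumed r = 0.5 this is 2 × [1 − Φ(2.77)] = 0.0056, or 0.0028 favourable. Any of three independent tests then gives 1 − (1 − 0.0028)³ = 0.8%, and any of six gives 1.7%. The absolute rates fall, but the multiple for three tests stays near 3 (0.83% / 0.28%).

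**Not counted:** running each outcome both unadjusted and in regression could add further chances. These analyses reuse the same data, so the increment was not calculated.

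**The case against.** The strongest reply is that this is a pilot and the 'or' sentence is a rationale. It explains why the outcomes matter, speaks of what results might suggest, and contains no test, threshold or decision. The primary is still named, medication changes are still labelled secondary, and the paragraph ends with feasibility and the design of a later trial. A pilot need not divide its significance level among outcomes.

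Most of this stands, and it rules out several stronger readings that a reader might infer:

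- *That the 'or' sentence is a formal success rule displacing the primary outcome.* It is not. It weakens or bypasses the primary by letting other outcomes support the same conclusion.
- *That the plan sets P ≤ 0.05 as the standard for that conclusion.* It does not say so. The link is inferred from this being the only significance threshold given.
- *That three outcomes inflate the error more than three-fold.* They cannot. Larger multiples require TSQM domain scores to count separately. The plan says these will be analysed, but not that one domain alone would suffice.
- *That the actual error must exceed 5%, or even 2.5%.* Unpaired tests on paired data could bring the absolute rate below both.

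The reply does not remove the narrower point. A favourable statement about implementation should rest on a result named in advance, and the wording lets it rest on whichever of several unadjusted tests succeeds. Medication changes would be a weak sole basis in any case. Entry requires a medication change in the past 6 months, so the count may fall without any effect of testing. The overlap is partial, because entry counts any medication while the outcome counts PGx drugs or drugs in the same class.

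**Conclusion.** The concern holds in a limited form. The plan names one primary outcome but no single primary score, lets either of two non-primary outcomes support expanded implementation, and states no multiplicity control.

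If P ≤ 0.05 is the operative standard and each test holds its level, the chance of a false favourable signal is about two to three times that of one pre-named test. It is about four to five and a half times only if any TSQM domain may stand for satisfaction; the top of that range requires all six tests to be independent. The ranges depend on assumed correlations.

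This affects what the report may conclude, not the conduct of the study. It is worth correcting because the correction is small.

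**What to change.** Two edits to section 6, Feasibility data collection:

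1. State that the primary outcome is the change in TSQM global satisfaction score from baseline to 6 months after PGx testing.
2. Reword the 'or' sentence so that any statement that the results support expanded implementation rests on that primary result. State that TSQM domain scores, medication changes and perceived value are exploratory, will be reported as estimates with 95% confidence intervals to inform the later trial, and will not carry the claim alone.

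With one primary score the rate for the claim returns to 5% two-sided (2.5% favourable), provided the test holds its level. No division of the significance level is needed, so the primary loses no power. The descriptive feasibility measures (prescriber acceptance, turnaround time and cost) are unaffected.

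The cost is one or two sentences, and a lone favourable secondary result can no longer be headlined as support for implementation.
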